I have read and agree to Protocol OPS-C-001/D-FR-01072-001 entitled "an international multi-center, open-label study to evaluate safety, tolerability, biodistribution, dosimetry and preliminary efficacy of ¹⁷⁷Lu-OPS201 for the therapy of somatostatin receptor positive neuroendocrine tumours (NETs)" with Amendment 10.0. I am aware of my responsibilities as a coordinating investigator under the guidelines of Good Clinical Practice (GCP), local regulations (as applicable) and the study protocol. I agree to conduct the study according to these guidelines and to appropriately direct and assist the staff under my control, who will be involved in the study.

NAME: PPD
TITLE: COORDINATING INVESTIGATOR SIGNATURE:

DATE:
OFFICE:

PPD
[name]
[name]
Switzerland
Phone: PPD
E-mail: PPD

SUMMARY OF CHANGES

The current version of the protocol was released on 10 August 2020 and includes Amendment 10.0. For all protocol amendments, amendment forms were prepared and are provided in the appendices listed in [Table 1](#). All modifications (except minor changes) are presented in the appendices.

Table 1 List of Protocol Amendments

Version number	Release date	Amendment form
3	29 April 2016	Appendix 6
4	04 October 2016	Appendix 7
5	03 November 2017	Appendix 8
6	27 February 2018	Appendix 9
7	24 July 2018	Appendix 10
8	07 May 2019	Appendix 11
9	13 August 2019	Appendix 12
10	10 August 2020	Appendix 13

SYNOPSIS

Name of sponsor/company: IPSEN PHARMA	
Name of finished product: ^{177}Lu -OPS201 - ^{177}Lu -satoreotide tetraxetan	
Name of active ingredient(s): ^{177}Lu -OPS201 - INN for OPS201 is satoreotide tetraxetan	
Title of study: An International Multi-Center, Open-Label Study to Evaluate Safety, Tolerability, Biodistribution, Dosimetry and Preliminary Efficacy of ^{177}Lu -OPS201 for the Therapy of Somatostatin Receptor Positive Neuroendocrine Tumours (NETs)	
Study number: OPS-C-001 / D-FR-01072-001	
Number of planned centres: 20	
Planned study period: January 2016 to November 2022	Phase of development: Phase I/II
Study type: Interventional, open-label, safety, tolerability, biodistribution, dosimetry and preliminary efficacy study	
Objectives:	
Primary study objective:	
To assess the safety and tolerability of peptide receptor radionuclide therapy (PRRT) with ^{177}Lu -OPS201 administered in three cycles in subjects with somatostatin receptor (sstr)2 positive NETs (including pheochromocytomas and paragangliomas).	
Secondary study objectives	

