1.2.5 Study duration

The estimated core trial duration of Part A is 18 to 21 months (for all subjects) including 6 to 10 months of treatment for a single subject, while the long-term follow-up lasts for up to 2 years after the EOCT/EW Visit.

The estimated core trial duration of Part B is 14 to 20 months (for all subjects) including 6 to 10 months of treatment for a single subject, while the long-term follow-up will last for up to 2 years after the EOCT/EOAC/EW Visit.

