For investigator data, the DCR rate at selected timepoints (Month 12, 18, 24) will also be generated. For DCR at month 12 (resp. 18 and 24 month), the analysis will include all patients who are on study at month 12 (resp. 18 and 24 month) defined as 365 days – 28 days (resp. 545 - 28 and 730- 28) relative to the first dose or patients who had early PD or death prior to that time. The best overall response category of CR, PR or SD in patients who have not had an early PD or death up to the timepoint will represent the subjects with disease control

c) Sum of Diameters

Descriptive statistics and 95% CIs of the mean for percentage change from baseline will be calculated by study part, cohort (part B only) and overall at Follow-up Visit 2, EOCT, EOAC (if any) and Long-Term Follow-up visits on the ITT and PP sets. The length of the longest diameter will also be presented.

Percent change and best percent change in sum of diameters will be listed.

Percent change of sum of diameters according to RECIST ^{CCI} will also be plotted by study part and cohort (part B only) at Visit 2, EOCT Visit, EOAC Visit (if any) and Long-Term follow up visits 1 and 2 on the ITT set.

Waterfall plots presenting best overall response (RECIST ^{CCI}) versus best percent change from baseline of sum of target lesion diameters over the whole study will be performed on the ITT set.

d) Progression Free Survival (PFS) from independent central review and from investigator assessment

PFS, defined as the time from first study drug administration to progression or death which ever occur first, will be analysed.

Disease progression will be assessed by tumour response evaluation according to RECIST v1.1/ ^{CCI}, measured using the same imaging technique (ceCT scan or MRI) for each subject throughout the study.

Event dates are assigned to:

- The first time when progressive disease was noted, or
- Date of death.

In case of progressive disease followed by death, the first event will be considered in the analysis. The date of progression will be recorded as the date of the last radiographic evaluation included in the series for that assessment.

Censoring dates are defined in subjects with no progressive disease or death before end of study or withdrawal. In these subjects, the censoring date is defined as the last date on which overall

RECIST status was evaluable. This is taken to be the date of the last radiological assessment at which the target lesions were evaluated (see Table 7).

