3.2.17 Interim analysis

1st Interim analysis

A first interim analysis will be conducted at the cut-off date of 27 September 2019 to inform the design of the chemotherapy combination study which has been added to the investigational plan.

The tables, listings and figures that will be produced for this analysis are flagged “*” in Section 7.2 – List of TFLs.

2nd Interim analysis

A second interim analysis of Part B data will be conducted at the EOCT/EOAC/EW (whichever occurs last) after completion of Cohorts 3 and 6. This will provide confirmation of the peptide dose to allow future studies to be developed. It will also confirm if Cohorts 2 or 7 and 8 will be initiated.

3rd Interim analysis

A third interim analysis, including all dosimetry, safety and efficacy data, will be performed after the EOCT/EOAC/EW (whichever occurs last) when the two study parts are completed.

The interim analyses may be combined based on the overall study status and subject accrual. The final analysis will be performed at the end of the 2-year long-term follow-up period.

Other analyses

In addition, dosimetry evaluation will be performed on an ongoing basis. After the first six subjects included have completed the study Part A (EOCT or Early Withdrawal Visit) an SRC meeting will be held before exposing the remaining subjects to the entire number of planned administrations. Safety data obtained until 8 weeks after the last administration of the 6th subject will be evaluated during this SRC. Prior to Part B, the SRC will review the safety and dosimetry data of the first six subjects included in Part A.

For Part B, a DRB meeting will be held to review the safety and radiation exposure data and decide whether to proceed with the enrolment of the next cohort dose level and the cumulative radioactivity within a cohort. Each dose escalation (both peptide and radioactivity) will be carefully evaluated by a DRB.

In addition, the SRC/DRB can be convened at any time during the trial to discuss potential safety issues. The data set to be reviewed by the SRC/DRB is specified in a specific charter.

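### Landmark disease control at months 12, 18 and 24 counts every early failure but omits event-free subjects with short follow-up, so it runs low, materially so if tabulated at the third interim

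*SAP*

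**What the plan says.** SAP Section 3.2.3(b) adds landmark rates to the disease control rate (DCR), for investigator data only. Two groups enter the denominator. For the first, "the analysis will include all patients who are on study at month 12" (and likewise at months 18 and 24), with the landmark "defined as 365 days – 28 days (resp. 545 - 28 and 730- 28) relative to the first dose". The second is added by the words "or patients who had early PD or death prior to that time". A success is a best response of CR, PR or SD "in patients who have not had an early PD or death up to the timepoint". Subjects with early events need not have started treatment any minimum time before the data cut-off, and no separate rule is given for interim analyses.

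On timing, SAP Section 3.2.17 states: "A third interim analysis, including all dosimetry, safety and efficacy data, will be performed after the EOCT/EOAC/EW" visit, whichever is last, once both parts are complete. The final analysis follows the 2-year long-term follow-up. SAP Section 3.2.14 places the End of Core Trial (EOCT) visit at week 24.

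For PFS, SAP Section 3.2.3(d) specifies Kaplan-Meier estimation with the median and its 95% CI, event counts and plots. It lists no progression-free proportions at fixed times.

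**The concern.** The two halves of the denominator have different entry conditions. An event-free subject must have been followed to day 337, 517 or 702. A subject with an event enters however short the follow-up. Take two subjects first dosed on the same day, six months before a data cut: the one who progressed at month 4 counts as a failure at months 12, 18 and 24, and the one doing well appears nowhere. Failures are therefore over-represented whenever follow-up is incomplete.

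The result would be a durable-control figure that partly reflects calendar time and drop-out. It could also distort comparisons between cohorts, because efficacy tables are presented by cohort and the cohorts start at different times. Under SAP Table 9, Cohort 4 does not recruit until Cohorts 1, 3 and 6 are full, and Cohort 5 follows Cohort 4. Later cohorts at higher activity would have shorter follow-up and so a larger downward bias.

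**Working it through.** The plan states no expected landmark rate, so there is no figure to reproduce. The cut-off days are 365 − 28 = 337, 545 − 28 = 517 and 730 − 28 = 702, or 11.07, 16.99 and 23.06 months at 30.4375 days per month.

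**Formula.** Let T be time to PD or death, C the available follow-up and t the landmark. The rule estimates O/(O + E), where O = P(T ≥ t and C ≥ t) and E = P(T < min(C, t)). The target is S(t) = P(T ≥ t). Subjects with C < t who are still event-free are in neither O nor E.

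**Assumptions.** PFS is exponential with median m; C is uniform; every event-free subject has at least SD; the interim calculation has no drop-out. The documents give no expected PFS, so m runs from 12 to 36 months.

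**Follow-up at the third interim, Part B.**
- Shortest: EOCT at week 24 = 168 days = 5.5 months, for a subject with three cycles on schedule.
- Longest, from dates: the protocol synopsis gives "Planned study period: January 2016 to November 2022". Two years earlier is November 2020. Taking the release of protocol version 6 (27 February 2018) as the earliest Part B start gives about 33 months.
- Longest, from SAP Section 1.2.5: a Part B core duration of 14 to 20 months.

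**Worked case: m = 24, C from 5.5 to 33, t = 23.06.**
- S(t) = 2^(−23.06/24) = 51.4%.
- Share with C ≥ t: (33 − 23.06)/27.5 = 36.1%. O = 0.361 × 0.514 = 18.6%.
- E from those subjects: 0.361 × 0.486 = 17.6%.
- E from the other 63.9%: 0.639 × {1 − [2^(−5.5/24) − 2^(−23.06/24)] / [(ln 2/24) × 17.56]} = 0.639 × 0.331 = 21.1%.
- Rule: 18.6/(18.6 + 38.7) = 32%, against a true 51%. The remaining 100 − 18.6 − 38.7 = 42.7% of subjects are event-free and uncounted.

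**Third interim, Part B (true % → rule %).**

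| Follow-up (months) | Median PFS | Month 12 | Month 18 | Month 24 |
|---|---|---|---|---|
| 5.5–33 | 12 | 53 → 48 | 37 → 28 | 26 → 13 |
| 5.5–33 | 24 | 73 → 69 | 61 → 51 | 51 → 32 |
| 5.5–33 | 36 | 81 → 78 | 72 → 63 | 64 → 45 |
| 5.5–20 | 24 | 73 → 64 | 61 → 30 | 51 → 0 |
| 5.5–14 | 24 | 73 → 52 | 61 → 0 | 51 → 0 |

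The zeros follow from the definition. Twenty months is 609 days, short of 702, and 14 months is 426 days, short of 517, so only early events remain in the denominator. They assume the cut falls at the end of the core period. Two additional cycles in the last subject would add 16 weeks, and 609 + 112 = 721 days would let the first-enrolled subjects just pass day 702.

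**Final analysis.** Subjects who stay in follow-up reach at least 56 + 730 = 786 days (one cycle) or 168 + 730 = 898 days (three cycles). Both exceed 702, so only drop-out matters. With event hazard h = ln 2/20 and drop-out hazard λ = −ln(0.9)/12 = 0.00878, drop-out by month 24 is 1 − 0.9² = 19%. Then O = exp[−(h + λ)t] and E = [h/(h + λ)](1 − O). At t = 23.06, O = 36.7% and E = 50.5%, so the rule gives 42.1% against a true 45.0%. At months 12 and 18 it gives 67.0% against 68.1%, and 53.5% against 55.5%. Month-24 shortfalls for other assumed drop-out: about 1 point with 5% by month 12 (10% by month 24), and 6 points with 20% (36% by month 24).

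**Check of the remedies.** In 20,000 simulated sets of 40 subjects (m = 24, follow-up 5.5–33), Kaplan-Meier and a ratio limited to subjects with potential follow-up ≥ t both returned 73%, 61% and 51–52%, matching the truth. With follow-up ending at 20 months, carrying the Kaplan-Meier curve forward to month 24 returned 57% against a true 51%, so that landmark has to be shown as not estimable.

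**The case against.** The strongest reply is that the documents do not show this table being produced at an interim. The list of outputs in SAP Section 7.2 is blacked out in the public copy. Section 3.2.3(b) ties investigator-assessed DCR to the end of long-term follow-up, so landmark DCR could be meant for the final analysis, where the bias is small. That stands as a limit on certainty. Against it, Section 3.2.17 says the third interim covers all efficacy data and exempts nothing.

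Second, median PFS, uniform follow-up and the Part B start date are assumptions. They move the size but not the direction.

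Third, Kaplan-Meier PFS is already planned, the study is descriptive, and 40 subjects give wide intervals. All true. But the planned PFS tables do not give the landmark proportions that would correct the ratio. At month 24 a 19-point shortfall is also well beyond the sampling error: near 45%, one standard error with 40 subjects is √(0.45 × 0.55/40) = 7.9 points.

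A reader might infer that the landmark rate is badly wrong at every analysis and in both parts. The documents do not support that. Subjects who remain in follow-up pass day 702 before the final analysis. Part A enrolled earlier and should be little affected. Month 12 is only 3–5 points low under the calendar dates.

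**Conclusion.** The denominator is asymmetric as written and, under non-informative censoring, biases landmark DCR downward whatever the true PFS.

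- **Third interim, if the table is produced there:** material, mainly for Part B at months 18 and 24. Shortfalls are about 3–5, 9–10 and 13–19 points at months 12, 18 and 24, assuming exponential PFS with median 12–36 months and uniform follow-up of 5.5–33 months. If Part B keeps to its stated core duration and the cut comes at its end, month 24 is 0% once any early event exists.
- **Final analysis:** about 1, 2 and 3 points, from drop-out alone, with 10% drop-out by month 12 and median PFS 20 months. At month 24 that is under half a standard error for 40 subjects.

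Whether landmark DCR was also intended for the first interim cannot be seen.

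**What to change.** At interim and final analyses, report the investigator-assessed Kaplan-Meier progression-free proportion at 12, 18 and 24 months with 95% CI, taken from the PFS analysis already planned. Label it as a progression-free proportion, since DCR also requires a qualifying best response. Print "not estimable" where the landmark lies beyond follow-up.

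If a DCR ratio is kept, restrict events and non-events alike to subjects first dosed at least the landmark time before the data cut-off. This removes the bias from short follow-up; drop-out would still need a stated rule.

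The cost is a small SAP revision and a few table rows, with no new data. The Kaplan-Meier figure carries the censoring rules of SAP Table 7, including censoring for undocumented progression and for non-permitted therapy. These may be informative and should be footnoted.

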1.3.1.3 Delay of administration and withdrawal from treatment

Part A

If any of the following occur, no further ¹⁷⁷Lu-OPS201 treatment will be administered:

- Subject withdraws his/her consent to further treatment
- Cumulative kidney dose exceeds 23 Gy
- Cumulative bone marrow dose exceeds 1.5 Gy as determined by image based dosimetry
- Absolute neutrophil count < 1.000*10⁹ /L (i.e. Grade 3 or higher)
- Platelets < 50.0*10⁹ /L (i.e. Grade 3 or higher)

- If one of the following medical conditions occurs (based on CTCAE v5.0) and does not resolve within 4 weeks (resolved=toxicity Grade 2 or lower and is at the discretion of the investigator):
 - Estimated glomerular filtration rate (eGFR) of < 45mL/min
 - Liver function tests (total bilirubin, aminotransferases) higher than Grade 3 (unless there is treatment-related liver toxicity, in which case the study treatment should be stopped or interrupted to enable recovery when deterioration of the liver function is noted);
 - Any other adverse event above Grade 2, except hair loss

The investigator can decide at his/her discretion to discontinue the treatment or to reduce the administered radioactivity for further safety reason than those here listed above to prevent a patient from higher grade toxicity.

Before the administration of Cycles 2 and 3 these criteria must be checked. In the event of withdrawal (discontinuation) from treatment only the Early Withdrawal (EW) Visit and the Long-term Follow-up will be performed (with the EW Visit 8 weeks after the last administration of ¹⁷⁷Lu-OPS201).

In some cases, cumulative absorbed dose to the bone marrow or kidney may be difficult to evaluate. If there is uncertainty about the radiation dose received to critical organs, but without substantial toxicity, the decision to administer additional cycles is left at the investigator's and subject's discretions. The decision may be either to stop the treatment, administer the full dose or a reduced dose depending on the benefit-risk balance for the subject.

In the situation of persisting Grade 3 and higher bone marrow, toxicity, a bone marrow aspirate can be considered if at the discretion of the investigator this could contribute to the evaluation of the event.

Part B

If any of the following occur, no further ¹⁷⁷Lu-OPS201 treatment will be administered:

- subject withdraws his/her consent to further treatment;
- cumulative kidney dose exceeds 23 Gy;

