Although a subject is not obliged to give reason(s) for withdrawing, if a subject is discontinued at any time after entering the study, the investigator should make a reasonable effort to ascertain the reason(s) while fully respecting the subject's rights. The investigator will make every effort to contact the subject and complete the termination status page on the eCRF and if possible conduct an EW Visit that will take place 8 weeks after the last administration study medication. In case of discontinuation of treatment/withdrawal from treatment, the EW Visit and the Long-term Follow-up Visits will be performed as planned.

The reasons for treatment and/or study discontinuation should be collected.

Appropriate follow-up of withdrawn subjects will be performed, as required. Attempts to contact subjects who withdraw from a study must be documented.

Withdrawn patients will be replaced if they do not complete treatment (the first three cycles) due to any reason other than exceedance of organ dose limits, treatment-related safety issues or disease progression.

1.3.6 *Schedule of assessments*

The schedule of assessments is provided in the study flow chart in [Table 2](#) for Part A and [Table 3](#) for Part B.

Extra visits, examinations, tests and interventions can be performed at any time if clinically indicated, as judged by the Investigator.

If the COVID-19 pandemic prevents subjects from coming to the site, subjects can have their study visit assessments performed remotely as judged appropriate by the investigator. This must be discussed with the sponsor before being implemented. In such a case, the investigator will perform a telemedicine visit and will make every effort, where applicable, to contact the subject's general practitioner or specialist physician to ensure all important medical information and safety event(s) occurring since the last visit are collected. Guidance on how to collect protocol-planned assessments will be provided to the investigator in a separate document. This document will be filed in the electronic trial master file. IECs/IRBs will be notified of the changes as applicable locally. Of note, as the adapted visit deviates from the regular protocol plan, the changes will be recorded as protocol deviations related to COVID-19.

Table 2 Study Procedures and Assessments Part A

	Screening Visit	Visit 1						FU Visit 1	Visits 2/3						FU Visits 2 + 3[a]	End of Core Trial Visit/ EW Visit[b]	LTFU Visits (up to 2 years)

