The DCR is defined as the proportion of participants who achieved a Complete Response (CR), a Partial Response (PR) or a Stable Disease (SD) as best overall response according to RECIST v1.1 criteria in the ITT Set. Subjects with no tumour assessment after the start of study treatment will be considered as with no disease control.

- Sum of diameters as percentage change

- Percentage change from baseline in the target lesions identified in the RECIST v1.1 assessment and/or the initial lesion(s) identified at eligibility as being >20 mm in diameter, calculated as:

$$\text{Percentage change from baseline} = \frac{(D_i - D_0)}{D_0} \times 100$$

With

D_i the sum of the longest diameters of the target lesions as per RECIST v1.1 at the time point/Visit i .

D_0 the sum of the longest diameters of the target lesions as per RECIST v1.1 at baseline.

- Best percentage change from baseline in sum of target lesions longest diameters, calculated as:

$$\text{Best percentage change from baseline} = \frac{(D_{min} - D_0)}{D_0} \times 100$$

With:

D_{min} the minimum sum of the longest diameters as per RECIST v1.1 on all measurement time points.

D_0 the sum of the longest diameters of the target lesions as per RECIST v1.1 at baseline.

Correlations will be computed between dosimetry parameters (cumulative absorbed dose) and volume and diameter changes in lesions at the last visit of the core trial (EOCT or EACT or EW as applicable).

(b) Progression Free Survival (PFS)

PFS will be evaluated up to two years after the EOCT/EOAC Visit and will be based on RECIST v1.1 status assessed by investigator assessment. PFS will be assessed by independent central review up to EOCT/EOAC/EW Visit (during the core study part).

PFS is defined as the time from start of study treatment until occurrence of tumour progression or death.

(c) Quality of life using EORTC QLQ C30 v3.0 and QLQ GLNET21 (2006) questionnaires.

- EORTC QLQ C30 v3.0

The European Organisation for Research and Treatment of Cancer (EORTC) score questionnaire (QLQ-C30) will be used for quality of life (QoL) evaluation.

Following the EORTC recommendations, fifteen scales can be derived from the initial 30 questions:

- A global health status/QoL scale,
- Five functional scales (physical, role, cognitive, emotional and social),
- Nine “symptoms” scales /items (nausea and vomiting, pain, fatigue, dyspnoea, insomnia, appetite loss, constipation, diarrhoea and financial difficulties).

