Table 7 Censoring Rules for PFS

Reason for censoring	Rule
No screening evaluable[a] assessment	Date of first treatment administration
Two or more not evaluable (NE) consecutive assessments before progressive disease or death	Date of last evaluable disease assessment before the second NE assessment
No progressive disease	Date of last evaluable disease assessment
Treatment discontinuation for undocumented progression	Date of last evaluable disease assessment
Treatment discontinuation for toxicity or other reason	Date of last evaluable disease assessment
Initiation of medications or therapy not permitted during the study	Date of initiation of non-permitted medication or therapy

a An assessment is considered NE when no imaging/measurement is done at all at a particular time point, or only a subset of lesion measurements are made at the time point. The subject is considered NE at that time point.

For central reading assessments, patients will be censored at the timepoint of the last central assessment at or before EOCT/EOAC.

The PFS time will be calculated as the time from first administration of the study drug to either progressive disease or death as follows.

$$\text{PFS time (in months)} = [(\text{Date of event} - \text{date of first administration of study drug} + 1) / 30.4375]$$

Data will be analysed by study part, cohort (part B only) and overall part B on the ITT and PP sets. The distribution of PFS times will be estimated using the Kaplan Meier method for each study part, cohort (part B only) and overall Part B. The median PFS time will be presented with its associated 95% CI, together with the number and percentage of events, by study part, cohort (part B only) and overall. The results will also be presented graphically in Kaplan Meier plots.

Completely missing tumour data: when tumour assessment visits are completely missing, FDA Guidance “Clinical Trial Endpoints for the Approval of Cancer Drugs and Biologics” [4] states that "events occurring after two or more missed radiological assessments will be censored in the analysis at the last adequate assessment”.

This will be implemented as follows:

[figure not shown]

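### SAP Table 7 makes stopping treatment for toxicity or other reasons a separate ground for censoring PFS; applied on its own, that row conflicts with the PFS definition and Table 8

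*SAP*

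**What the plan says.** SAP 3.1.6 defines the endpoint without reference to treatment status: "PFS is defined as the time from start of study treatment until occurrence of tumour progression or death". It adds that "PFS will be evaluated up to two years after the EOCT/EOAC Visit" on investigator assessment. SAP 3.2.3 makes the investigator's RECIST v1.1 assessment primary and the central read a sensitivity analysis.

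Follow-up does not end with treatment. SAP 1.3.5 says that after discontinuation "the EW Visit and the Long-term Follow-up Visits will be performed as planned". SAP 1.2.2 sets tumour assessments every 3 months until progression, 2 years after the EOCT, EOAC or EW visit, consent withdrawal, loss to follow-up or death.

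The censoring text in SAP 3.2.3(d) opens with "Censoring dates are defined in subjects with no progressive disease or death before end of study or withdrawal". Table 7 then lists reasons. One is that no progression occurred. Two others are "Treatment discontinuation for undocumented progression" and "Treatment discontinuation for toxicity or other reason". All three carry the same rule: "Date of last evaluable disease assessment". Table 8, Scenario 3, treats stable disease at the EOCT/EOAC/EW scan followed by progression in long-term follow-up as an event at the follow-up visit.

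**The concern.** If the discontinuation rows cover only subjects who never progress or die, they duplicate the no-progression row. They have an effect of their own only if they override a later event. Table 7 does contain rows that override: two or more consecutive non-evaluable assessments, and the start of non-permitted therapy. A programmer could reasonably treat the toxicity row the same way.

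The subjects concerned are unlikely to be a random subset. SAP 1.3.1.3 stops treatment for organ-dose limits, haematological toxicity and other adverse events, and such stops may be related to prognosis. Censoring there would be informative and would remove progressions already recorded. PFS is also reported by cohort, and most Part B cohorts have three to five subjects, so one lost event can change a cohort's result.

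**Working it through.** **Passages side by side.** Take a Part B subject who stops for toxicity after cycle 1, with no delays. The EW scan falls at 8 × 7 / 30.4375 = 1.8 months, with follow-up scans at 4.8 and 7.8 months. Disease is stable at the first two and progressive at the third.

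- Under the SAP 3.1.6 definition and the pattern of Table 8 Scenario 3, this is an event at 7.8 months.
- If the toxicity row stands alone, the subject is censored. The date is unclear, because the rule has no cut-off at discontinuation: it could be taken as the EW scan or as a later scan.
- The lead-in does not decide between them. SAP 1.3.1.3 writes "In the event of withdrawal (discontinuation) from treatment", which suggests that withdrawal can mean stopping treatment. SAP 1.3.5 separates withdrawal from treatment and from the study, and SAP 3.2.6 separates the treatment period from long-term follow-up.

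**Follow-up at stake.** A stop after cycle 2 puts the EW scan at 16 × 7 / 30.4375 = 3.7 months. Adding 24 months, the last of up to eight further scans falls at about 25.8 months (stop after cycle 1) or 27.7 months (stop after cycle 2).

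**Illustrative size.** The documents state no PFS median, event count or power, so there is no figure to reproduce. The inputs below are assumptions, except the scan schedule (Part B: weeks 8, 16 and 24, then every 3 months for 24 months after EOCT/EW).

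- Exponential PFS with hazard ln 2 / median; median 12, 18 or 24 months in subjects who complete treatment.
- 10%, 20% or 30% stop after cycle 1 or 2; their hazard is multiplied by 1, 1.5 or 2.
- No deaths, missed scans or new therapy; 20,000 simulated subjects per setting.
- Reading A counts every observed progression. Reading B censors stoppers at the EW scan unless progression was seen by then.
- Events lost per 55 subjects = 55 × (event proportion under A − event proportion under B).

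Results for 20% stoppers:

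| Assumed median | Hazard ratio | Events A | Events B | KM median A | KM median B | Lost per 55 |
|---|---|---|---|---|---|---|
| 12 | 1 | 81.2% | 68.6% | 13.8 | 14.5 | 6.9 |
| 12 | 1.5 | 83.9% | 70.0% | 11.5 | 14.5 | 7.7 |
| 12 | 2 | 84.5% | 71.1% | 11.5 | 14.5 | 7.4 |
| 18 | 1 | 66.9% | 56.0% | 20.5 | 20.5 | 6.0 |
| 18 | 1.5 | 70.0% | 57.4% | 17.5 | 20.5 | 6.9 |
| 18 | 2 | 71.8% | 57.9% | 17.5 | 17.5 | 7.7 |
| 24 | 1 | 56.5% | 47.4% | 26.5 | 26.5 | 5.0 |
| 24 | 1.5 | 59.1% | 47.6% | 23.5 | 26.5 | 6.3 |
| 24 | 2 | 61.7% | 48.9% | 22.8 | 26.5 | 7.1 |

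For example, 55 × (0.700 − 0.574) = 6.9. Over all 27 settings, Reading B drops 71% to 86% of the progressions observed in stoppers, or 2.6 to 11.4 events per 55 subjects. With hazard ratio 1 the median shifts by at most 14.5 − 13.8 = 0.7 months. With 1.5 or 2 it shifts by 0 to 26.5 − 22.8 = 3.7 months. Medians fall on scan dates, so most non-zero shifts equal one 3-month interval.

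**The case against.** A reader might infer that the SAP throws away observed progressions in early stoppers. The documents do not establish that. No sentence says that progression after stopping is ignored. The lead-in supplies censoring dates for subjects without progression or death, and withdrawal, paired there with end of study, may well mean leaving the study. Where Table 7 cuts follow-up short it says so explicitly, and the toxicity row has no such cut-off: for a stopper scanned for two years and never progressing, the last evaluable assessment is the final follow-up scan. Table 8 Scenario 3 makes no exception for stoppers. On this view the row is merely redundant.

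Most of this stands, and it is why the point is a conflict in the text rather than an established discard rule. It does not remove the conflict. Table 8 deals with missing data, pools EW with EOCT/EOAC and is silent on reasons for stopping. Precedence between Table 7 rows and a later event is nowhere stated.

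It is also tempting to delete both discontinuation rows. That goes too far. SAP 1.2.2 ends tumour assessments at clinical as well as radiological progression, so subjects stopped for undocumented progression may have few or no later scans, and that row tells the analyst how to handle them.

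The simulation also ignores censoring at new therapy, which tends to overstate the events lost.

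**Conclusion.** The point holds as a conflict in the text. Read as a stand-alone rule, the toxicity-or-other-reason row contradicts the PFS definition and Table 8 and would censor progressions observed after early stopping; read as redundant, it does no harm. Two programmers could follow this SAP and report different event counts and medians.

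The size depends on Reading B and on stopping rates, medians and hazard ratios that the documents do not give. If stopping is unrelated to prognosis, the cost is mainly lost events and precision. A material overstatement of the median needs stoppers to progress faster.

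The scope is limited. Central PFS is censored at or before EOCT/EOAC in any case, so only investigator PFS is exposed. It is a secondary, descriptive endpoint with no formal test, so no error rate or sample size is affected.

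**What to change.** In SAP Table 7, delete the toxicity-or-other-reason row, or limit it to subjects with no documented RECIST progression or death at any later assessment. Keep the undocumented-progression row with the same limit. Add one sentence stating that RECIST progression or death after treatment discontinuation counts as an event, subject to the existing rules on two or more missed or non-evaluable scans and on non-permitted therapy. In the lead-in, say whether withdrawal means withdrawal from the study. If censoring at discontinuation is of interest, report it as a labelled sensitivity analysis.

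The cost is SAP wording and the matching programming specification. The scans are already scheduled, so no new data are needed.
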